The purpose of this Statistical Analysis Plan (SAP) is to provide details of the statistical analyses that have been outlined within the protocol **superseded amendment 1** for study 20190008, Erenumab (AMG 334) dated **29 June 2022**. The scope of this plan includes the primary analysis that is planned and will be executed by the Amgen Global Biostatistical Science department unless otherwise specified.

2. Objectives, Endpoints and Hypotheses

2.1 Objectives and Endpoints

Object	ives	Endpoints
Primar	ъ	
•	To evaluate the treatment benefit of erenumab on headache duration of at least moderate pain intensity	 Change from baseline in mean monthly hours of at least moderate headache pain intensity over months 1, 2, and 3
Secon	dary	
•	To evaluate the treatment benefit of erenumab on functional impairment	 Change from baseline in mean monthly function domain score as measured by the Migraine Functional Impact Questionnaire (MFIQ) over months 1, 2, and 3: Impact on physical functioning Impact on usual activities Impact on emotional functioning Impact on social functioning
•	To evaluate the treatment benefit of erenumab on duration of migraine pain of at least moderate intensity	 Change from baseline in mean monthly average duration of at least moderate pain intensity in migraine attacks occurring over months 1, 2, and 3
•	To evaluate the treatment benefit of erenumab on peak migraine pain intensity	 Change from baseline in mean monthly average peak migraine pain intensity as assessed by the 11-point Numeric Rating Scale (NRS) over months 1, 2, and 3

Exploratory	
Main Double-blind Treatment Period (month	n 1 to 3)
To evaluate the treatment benefit of erenumab on duration of oral triptan-treated migraine attacks	 Change from baseline in mean monthly hours of at least moderate pain intensity for qualifying oral triptan-treated

	migraine attacks over months 1, 2, and 3
To evaluate the treatment benefit of erenumab on duration of migraine pain of at least moderate intensity for oral triptan-treated migraine attacks	 Change from baseline in mean monthly average duration of at least moderate pain intensity in qualifying oral triptan-treated migraine attacks occurring over months 1, 2, and 3
 To evaluate the treatment benefit of erenumab on migraine symptoms 	 Change from baseline in Migraine Symptom Severity Score (MSSS) total score at assessment time points
	 Change from baseline in the most troublesome symptom (MTS) at month 3
	 Change in Patient Global Impression of Severity (PGI-S) total score at month 3
	 Change from baseline in mean monthly total migraine freedom days over months 1, 2, and 3
 To evaluate the treatment benefit of erenumab on interictal burden of migraine 	 Change from baseline in Migraine Interictal Burden Scale (MIBS-4) total score at assessment time points
	 Achievement of no or mild interictal burden as measured by the MIBS-4 at assessment time points
 To evaluate the treatment benefit of erenumab on functional impairment 	 Change from baseline in headache impact scores as measured by the Headache Impact Test (HIT-6) total score at assessment time points
	 Change from baseline in physical function domain score as measured by MFIQ at assessment time points
	 Change from baseline in usual activities domain score as measured by MFIQ at assessment time points
	 Change from baseline in social function domain as measured by MFIQ at assessment time points
	 Change from baseline in emotional function domain score as measured by MFIQ at assessment time points
	 Change from baseline in overall impact on usual activities global

	1
	item score as measured by MFIQ at assessment time points
 To evaluate the treatment benefit of erenumab on headache-related cognitions and beliefs 	 Change from baseline in pain catastrophizing as measured by the Pain Catastrophizing Scale (PCS) at month 3
 To evaluate the treatment benefit of erenumab on monthly migraine days (MMD) 	Change from baseline in mean MMD over months 1, 2, and 3
Following 2 endpoints will be calculated attack	from months with at least 1 migraine
• To evaluate the treatment benefit of erenumab on duration of migraine pain of at least moderate intensity with at least 1 migraine attack	Change from baseline in mean monthly average duration of at least moderate pain intensity per migraine attack occurring over months 1, 2, and 3
 To evaluate the treatment benefit of erenumab on peak migraine pain intensity with at least 1 migraine attack 	Change from baseline in mean monthly average peak migraine pain intensity as assessed by the 11-point Numeric Rating Scale (NRS) over months 1, 2, and 3
Exploratory Double-blind Treatment Phase	
To evaluate the treatment benefit of erenumab on interictal burden of migraine	• Change from baseline in Migraine Interictal Burden Scale (MIBS-4) total score at month 4
For the first qualifying oral triptan-treated assessment:	d attack with complete data at 2-hour
To evaluate the treatment benefit of erenumab on achieving and sustaining pain freedom following treatment with an oral triptan	 Achievement of pain freedom at 2 hours post-triptan dose for the first attack at month 4 Achievement of 24-hour sustained pain freedom post-triptan dose for the first attack at month 4
	 Achievement of pain freedom at 30 and 60 minutes post-triptan dose for the first attack at month 4
To evaluate the treatment benefit of erenumab on achieving pain relief following treatment with an oral triptan	 Achievement of pain relief at 30, 60, and 120 minutes post-triptan dose for the first attack at month 4
 To evaluate the treatment benefit of erenumab on achieving freedom from the most bothersome symptom following treatment with an oral triptan 	 Achievement of freedom from the most bothersome symptom at 30, 60, and 120 minutes post-triptan dose for the first attack at month 4
To evaluate the treatment benefit of erenumab on achieving relief from the most bothersome	Achievement of relief from the most bothersome symptom at 30,

symptom an oral tri	following treatment with otan		60, and 120 minutes post-triptan dose for the first attack at month 4
of erenum	te the treatment benefit lab on migraine e following treatment with otan	•	Migraine recurrence within 24 hours post-triptan dose for the first attack at month 4
To evalua of erenum rescue me treatment For the first qua	te the treatment benefit ab on use of migraine edication following with an oral triptan lifying oral triptan-only-t i	• reated a	Use of migraine rescue medication within 24 hours post-triptan dose for the first attack at month 4 attack with complete data at
2-hour assessm		1	
benefit of achieving freedom	ate the treatment ferenumab on g and sustaining pain following treatment triptan only	•	Achievement of pain freedom at 30, 60, and 120 minutes post- triptan dose for the first triptan- only-treated attack in which complete data is obtained (at least 2 hours timepoint) at month 4
benefit of achieving	ite the treatment erenumab on pain relief following t with oral triptan only	•	Achievement of pain relief at 30, 60, and 120 minutes post- triptan dose for the first triptan- only-treated attack at month 4
To evaluate benefit of achieving most bot	te the treatment erenumab on freedom from the hersome symptom treatment with oral	•	Achievement of freedom from the most bothersome symptom at 30, 60, and 120 minutes post- triptan dose for the first triptan- only-treated attack at month 4
To evaluate benefit of achieving botherso	te the treatment Ferenumab on Frelief from the most me symptom following t with oral triptan only	•	Achievement of relief from the most bothersome symptom at 30, 60, and 120 minutes post- triptan dose for the first triptan- only-treated attack at month 4

2.2 Hypotheses and/or Estimations

The primary clinical hypothesis is that preventive treatment with monthly administration of erenumab is superior to placebo in reducing **duration of moderate or severe** headache pain in subjects with high-frequency episodic migraine (HFEM) who have previously failed at least 1 migraine preventive treatment.

3. Study Overview

3.1 Study Design

Study 20190008 is a phase 4, interventional, prospective, double-blind, randomized, placebo-controlled, multicenter global study, evaluating the effects of erenumab on

aspects of migraine beyond MMD reduction in adult subjects with high-frequency episodic migraine (HFEM) who have previously failed at least 1 preventive treatment.

Subjects who meet eligibility criteria will be enrolled in a run-in period (2 weeks in duration) during which they will record oral triptan-treated migraine attacks in an episode electronic diary (eDiary). At the end of the run-in period, subjects will be eligible to enter the 4-week baseline period only if they have 1 or more qualifying oral triptan-treated migraine attacks (defined as migraine attacks of at least moderate peak pain intensity that are treated with an oral triptan within 2 hours of pain reaching at least moderate severity) and if pain freedom is not achieved within 1 hour following oral triptan intake for > 50% of their qualifying migraine attacks. During the baseline period subjects will keep a daily eDiary. At the end of the baseline period, subjects who meet specific eligibility criteria will be able to enter the double-blind treatment period (DBTP).

The 4-month DBTP has 2 phases:

- Main DBTP (M-DBTP, months 1-3) that will assess the effect of erenumab on metrics such as time spent in at least moderate pain, peak migraine severity, and functional impairment
- Exploratory DBTP (E-DBTP, month 4) that will assess the impact of erenumab on the acute response to treatment with oral triptans **therapy** as well as non-ictal burden

Throughout both phases of the DBTP, investigational product will be administered every 4 weeks (Q4W). Data entry will follow a daily eDiary collection during the M-DBTP and transition to an episode eDiary during the E-DBTP.

3.2 Sample Size

A total sample size of 576 subjects (288 subjects per group including 10% dropouts) provides at least a 90% power for the primary efficacy hypothesis. The statistical power for secondary efficacy hypotheses ranges from 81% to > 99% (Table 3-1).

Table 3-1. Sample Size Assumptions and Statistical Powers for Primary and
Secondary Efficacy Endpoints for a Total Sample Size of 576 Subjects
Including a 10% Attrition Rate due to Dropout

Hypothesis	Assumed Treatment Effect	Power
------------	--------------------------------	-------

	(Common SD)	
Primary:	-16.7 (50)	96%
Change from baseline in mean monthly hours of at least moderate headache pain intensity over months 1, 2, and 3		
Secondary: Change from baseline in mean monthly		
MFIQ physical function domain score over months 1, 2, and 3	-9.2 (18.0)	> 99%
MFIQ usual activities domain score over months 1, 2, and 3	-7.5 (19)	> 99%
MFIQ emotional function domain score over months 1, 2, and 3	-11.5 (22)	> 99%
MFIQ social function domain score over months 1, 2, and 3	-6.9 (20)	97%
Average duration of at least moderate migraine pain intensity in migraine attacks occurring over months 1, 2, and 3 ^a	-2.0 (8)	81%
Average peak migraine pain intensity over months 1, 2, and 3	-0.11 (0.44)	81%

MFIQ = Migraine Functional Impact Questionnaire

Note: All power calculations are based on a 2-sided significance level of 0.05. The assumed treatment effects and common standard deviations are derived or chosen from a subset of placebo-treated and erenumab-140mg-treated subjects in erenumab Study 20120296 with high-frequency episodic migraine (ie, 7 to 14 monthly migraine days) and having at least 4 moderate-to-severe migraine attacks at baseline. ^a If a subject did not have any migraine attacks in a given month, the duration of at least moderate migraine pain intensity **was counted as 0**.

4. Covariates and Subgroups

4.1 Planned Covariates

For efficacy endpoints of the M-DBTP, all model-adjusted analyses of efficacy endpoints will include the corresponding baseline value for the endpoint being analyzed. The baseline value is calculated based on data collected during the 4-week baseline period or on day 1 prior to the first dose.

For pain freedom and pain relief related efficacy endpoints of the E-DBTP (month 4), the following covariates may be considered:

• Medication overuse status at month 3 (yes vs no)

- Time to triptan intake since reaching moderate/severe pain of the first qualifying attack at month 4 (< 1 hour vs ≥ 1 hour)
- Pain intensity prior to triptan intake is severe (yes [NRS ≥ 7] vs no) of the first qualifying attack at month 4

For most bothersome symptom related endpoints of the E-DBTP, the following symptom types may be included in the model:

- Nausea/Vomiting (yes vs no)
- Photophobia/phonophobia (yes vs no)

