- ^c The day 1 visit (randomization day) must occur 29 to 35 days after baseline entry. Study visits after day 1 may be completed within ± 3 days of the scheduled visit. All study visit target dates are to be calculated from the day 1 study date. All study procedures for a given study visit are to be completed on the same day (see Section 8.1.4).
- ^d The end of study visit occurs at week 16 or 4 weeks after last dose of investigational product for subjects who discontinue the study. If a subject discontinues treatment or the study prior to week 12, the week 12 assessments should be conducted for their early termination visit (see Section 8.1.5).
- At the start of the baseline period, data collected during the run-in period will be assessed to determine if the subject meets the eligibility criteria to enter the baseline period. On day 1, data collected during the baseline period will be assessed to determine if the subject meets the eligibility criteria to enter the double-blind treatment period.
- ^f For subjects who provided informed consent for the pharmacogenetic studies, DNA will be obtained from the cell pellet collected in the plasma tube used for the biomarker development sample. Therefore, additional sampling is not required.
- ⁹ The episode eDiary will be collected based on episodes during the run-in period and during weeks 13 to 16.

2. Introduction

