5.1 Inclusion Criteria

Subjects are eligible to be included in the study and enter the run-in period only if all of the following criteria apply:

- 101 Have provided informed consent prior to initiation of any study specific activities/procedures.
- 102 Age \geq 18 years upon entry into initial screening.
- 103 Documented history of migraine with or without aura according to the International Headache Society (IHS) International Classification of Headache Disorders, Third Edition (ICHD-III) for ≥ 12 months.
- 104 Have HFEM: Defined as history of \geq 7 to < 15 migraine days and < 15 headache days per month on average during the 3 months prior to screening.
- 105 History of \geq 4 migraine attacks of at least moderate severity per month on average during the 3 months prior to screening.
- 106 History of treatment failure with at least 1 preventive treatment for migraine. Failure of preventive treatment for migraine is defined as treatment discontinuation due to lack of efficacy, adverse event, or general poor tolerability.
- 107 Regular use of an oral triptan (using only eletriptan, rizatriptan, sumatriptan, or zolmitriptan) for acute migraine treatment, and typically initiating acute treatment with an oral triptan on > 50% of attacks of at least moderate pain intensity. Regular use is defined as ≥ 4 days of oral triptan use per month during the 3 months prior to screening.

Subjects are eligible to enter the baseline period of the study only if they have completed

the run-in period and the following criterion applies (based on the episode eDiary):

108 Have at least 1 qualifying triptan-treated migraine attack during the run-in period (using 1 of the specified 4 oral triptans from inclusion criteria 107) where pain freedom has not been achieved within the first hour from triptan intake during that migraine attack. If a subject reports more than 1 qualifying oral triptan-treated migraine attack where for > 50% of migraine attacks during the run-in period pain freedom is not achieved in ≤ 1 hour following oral triptan intake during that migraine attack, the subject will be eligible to enter the 4-week baseline period.

Subjects are eligible to enter the DBTP of the study only if they have completed the

baseline period and all of the following criteria apply (based on daily eDiary):

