5.1.2 Efficacy Endpoints Based on Episodic Diary Data Collection During E-DBTP

During the 2-week run-in period and the 1-month E-DBTP at month 4, subjects experiencing a qualified triptan-treated migraine attack will report medication usage, pain intensity, the most bothersome symptom and corresponding severity using the episodic diary. A qualifying headache for reporting is a headache reaching at least moderate pain intensity with initial triptan intake within 2 hours and also satisfying migraine headache criteria (ie, a qualified triptan-treated migraine attack). The initial triptan intake time (ie, time point 0) will trigger a 48-hour assessment window, during which the headache pain intensity, severity of the most bothersome symptom at 30, 60 and 120 minutes, 24 hours and 48 hours post triptan will be collected. Another 48-hour assessment window will be triggered if there is a new qualified triptan-treated migraine attack starts after the previous assessment window.

Headache Pain Intensity (NRS) in E-DBTP

Worst or peak pain intensity collected on a headache ranges from 0 to 10 with a higher score indicating more severe pain.

NRS Pain intensity is collected when a qualified headache reaching at least moderate pain intensity with triptan intake within 2 hours and for the following timed assessments at 30 minutes, 1-hour, 2-hour, 24-hour and 48-hour diaries.

Migraine Rescue Medication

Migraine rescue medication for each qualifying triptan-treated attack is defined as any additional acute headache medication(s) taken during the 48-hour assessment window.

Migraine Recurrence Within 24 Hours Post-triptan

Pain intensity NRS = 0 at any of the 30-minute, 60-minute, and 2-hour timed assessments and pain intensity NRS \geq 4 at 24-hour timed assessment

Pain Relief at timed assessment post-triptan dose

Pain intensity NRS < 4 at the specific timed assessment (eg, 30 minutes, 60 minutes, or 2 hours post-triptan dose).

Pain freedom at timed assessment post-triptan dose

Pain intensity NRS = 0 at the specific timed assessment (eg, 30 minutes, 60 minutes or 2 hours post-triptan dose).

Achievement of 24-hour sustained pain freedom post-triptan dose

Pain intensity NRS = 0 at both 2-hour and 24-hour timed assessment without rescue medication taken post-triptan dose.

Most Bothersome Symptom

The most bothersome symptom can be selected among nausea, vomiting, sensitivity to light, or sensitivity to sound.

Severity of Most Bothersome Symptom (4-level)

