5.3 Study Points of Reference

Run-in Assessment

Run-in assessment is designed to determine the entry eligibility for baseline period.

Baseline Assessment

Baseline assessment for the endpoint of the interest is defined as the last non-missing measurement taken or the monthly interval assessed (for endpoints derived from daily eDiary collection during baseline period) before the first dose of investigational product. In cases where baseline measurements are taken on the same day as IP, it will be assumed that these measurements are taken prior to IP being administered. For subjects who are randomized but not dosed after the randomization, the baseline of the study is defined as the last non-missing measurement prior to or on the date of randomization.

Study Day 1

Study Day 1 is defined as the first IP dose date. For subjects who are randomized but not dosed after randomization, the Study Day 1 is defined as the date of randomization.

Study Day

Study Day is defined as the number of days from Study Day 1.

Before Study Day 1:

Study Day = (Date of Interest – Date of Study Day 1)

On or after Study Day 1:

Study Day = (Date of Interest – Date of Study Day 1) + 1

Therefore, the day prior to Study Day 1 is -1.

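### Month-4 triptan-response models leave out the run-in response already collected on the same diary, while SAP 4.1 keeps open adjustment for covariates measured after randomisation

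*SAP*

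**What the plan says.** **Same instrument before and after treatment.** The footnotes to the Schedule of Activities (Protocol 1.3) state: "The episode eDiary will be collected based on episodes during the run-in period and during weeks 13 to 16". SAP 5.1.2 covers both periods: "During the 2-week run-in period and the 1-month E-DBTP at month 4, subjects experiencing a qualified triptan-treated migraine attack will report medication usage". It then describes a 48-hour window, opened by the first triptan intake, in which headache pain intensity and "severity of the most bothersome symptom at 30, 60 and 120 minutes, 24 hours and 48 hours post triptan will be collected".

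**A run-in attack for every eligible subject.** Inclusion criterion 108 (Protocol 5.1) begins: "Have at least 1 qualifying triptan-treated migraine attack during the run-in period". Where there are several attacks, SAP 3.1 admits a subject "if pain freedom is not achieved within 1 hour following oral triptan intake for > 50% of their qualifying migraine attacks".

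**Use made of the run-in.** SAP 5.3 says: "Run-in assessment is designed to determine the entry eligibility for baseline period". The baseline characteristics listed in SAP 9.4 do not include run-in response.

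**Month-4 models.** Table 9-3 gives a logistic model with treatment group only for 2-hour pain freedom, and footnote d extends it to the other month-4 endpoints named there. The rescue-medication row is also treatment only. SAP 4.1 ties baseline adjustment to the M-DBTP. For month-4 pain freedom and pain relief it says "the following covariates may be considered" and lists medication overuse at month 3, time to triptan intake in the month-4 attack, and "Pain intensity prior to triptan intake is severe (yes [NRS ≥ 7] vs no) of the first qualifying attack at month 4". Protocol 9.3.2 calls for the corresponding baseline value where applicable and does not limit this to months 1 to 3.

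**The concern.** Month 4 exists to ask whether erenumab improves the response to the subject's own triptan. The natural baseline for that question is the same response before treatment. It has been collected, and no month-4 triptan-response model uses it.

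The three covariates in SAP 4.1 all arise after randomisation. Peak migraine pain intensity is itself a secondary endpoint on which erenumab is expected to act, so pre-triptan severity in the month-4 attack may be part of the effect being measured. Month-3 overuse counts acute-medication days, which treatment may also change. Adjusting for a variable that treatment moves can remove part of the treatment effect.

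SAP 9.5 says that its tables give the covariates in the models, and Table 9-3 gives none for these endpoints. SAP 4.1 gives no rule for when its option applies, who decides, or whether the choice precedes unblinding. Models that can yield different odds ratios are therefore left open.

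**Working it through.** **1. The plan's own figure.** The documents give no power, event rate or effect size for any month-4 triptan-response endpoint. The only sizing figure to reproduce is for the primary endpoint: n = 288 × 0.9 ≈ 259 per arm, difference 16.7, SD 50, two-sided 0.05. Then z = 16.7 / (50 × √(2/259)) = 3.80, and power = Φ(3.80 − 1.96) ≈ 96.7%, against 96% stated. It reproduces, but it does not bear on the covariate question. Steps 3 and 4 rest on assumed inputs.

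**2. What criterion 108 does to early run-in pain freedom.** More than 50% of qualifying attacks must lack pain freedom within 1 hour.
- One attack: it must have failed at 1 hour.
- Two attacks: both must have failed, since 1 of 2 is not more than 50%.
- Three attacks: at least 2 of 3 must have failed.

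Run-in pain freedom at 30 or 60 minutes is therefore zero by design unless a subject had three or more qualifying attacks in a run-in of 14 to 18 days. Two-hour pain freedom is not screened directly and can vary.

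**3. Precision lost by omitting run-in response.** Simulation, 1,000 replicates per setting. Assumed: 259 per arm; nominal 2-hour pain freedom of 25% v 36%; 10% pain-free at 1 hour before screening; criterion 108 applied at run-in; a normal latent response sharing a subject effect between run-in and month 4. The covariate is the share of run-in attacks pain-free at 2 hours. Logistic regression, two-sided 0.05.

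| Latent within-subject correlation | Run-in attacks | Power, treatment only | Power, plus run-in response |
|---|---|---|---|
| 0.1 | 1 | 78.8% | 79.6% |
| 0.3 | 1 | 76.7% | 77.7% |
| 0.5 | 1 | 77.9% | 80.2% |
| 0.7 | 1 | 83.1% | 86.4% |
| 0.1 | 3 | 73.1% | 73.4% |
| 0.3 | 3 | 76.5% | 78.2% |
| 0.5 | 3 | 79.3% | 84.7% |
| 0.7 | 3 | 83.1% | 93.3% |

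Only the comparison within a row is informative. With one attack the gain is 0.8 to 2.3 points for correlations up to 0.5, and 3.3 points at 0.7. With three attacks it runs from 0.3 to 10.2 points.

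**4. What the optional severity adjustment would remove.** Assumed: 50% of placebo attacks severe before triptan; 30% pain-free in non-severe placebo attacks; odds ratio (OR) for pain freedom, severe v not, of 0.6 or 0.4; direct treatment OR 1.3. The adjusted model returns ln 1.3 = 0.262. The total effect averages each arm over its own severity mix.

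Example with severe OR 0.4 and 40% severe on erenumab. The non-severe placebo odds are 0.3/0.7 = 0.4286.
- Severe placebo: odds 0.4286 × 0.4, so 14.6%.
- Treated non-severe: odds 0.4286 × 1.3, so 35.8%.
- Treated severe: odds 0.4286 × 0.4 × 1.3, so 18.2%.
- Placebo overall: 0.5 × 30% + 0.5 × 14.6% = 22.3%.
- Erenumab overall: 0.6 × 35.8% + 0.4 × 18.2% = 28.8%.
- Total OR ≈ 1.405, ln = 0.340. Share removed = 1 − 0.262/0.340 ≈ 23%.

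| Severe on erenumab | Total OR (severe OR 0.6; 0.4) | Share of log-OR removed |
|---|---|---|
| 50% (no change) | 1.30; 1.29 | none |
| 45% | 1.33; 1.35 | 8%; 12% |
| 40% | 1.36; 1.41 | 15%; 23% |
| 30% | 1.43; 1.53 | 27%; 38% |

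With no change in severity, the adjusted log-OR is 1% to 4% larger than the total. That is the usual gap between conditional and marginal odds ratios.

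**The case against.** **The severity adjustment is not in any specified model.** This stands. SAP 4.1 is permissive, Table 9-3 is treatment only, and the SAP's list of changes records that covariates were taken out of the 2-hour pain-freedom model. A reader might infer that the plan will adjust for a mediator; the documents do not support that. What remains is an open option in 4.1 that the tables do not share.

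**Omitting a baseline covariate does not bias a randomised comparison.** This also stands. A reader might infer that the treatment-only odds ratio is biased because run-in response is missing from the model; it is not. There is one qualification. The analysis concerns the first qualifying attack in subjects who received the week-12 dose, and both conditions arise after randomisation. Run-in response by arm among those analysed would help show whether the groups stayed comparable, though adjusting for it would not cure all selection.

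**Other limits that stand.**
- Month 4 as a whole does not lack baseline adjustment. The month-4 MIBS-4 model in SAP 9.5.3 includes its baseline value.
- No stated rule is clearly broken. Protocol 9.3.2 applies only where applicable, and SAP 4.1 takes baseline from the 4-week baseline period or day 1, which follow the run-in.
- Nothing in the documents says that erenumab changes time to triptan intake.
- The endpoints are exploratory and outside the alpha-controlled sequence.

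**What the objection does not remove.** The pre-treatment measure is already collected, using it costs almost nothing, and SAP 4.1 and Table 9-3 still differ on covariates.

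**Conclusion.** The point holds as a low-cost improvement and a clean-up of the text, limited to the exploratory month-4 triptan-response endpoints. The specified analysis is valid without the run-in response. The loss is precision and is probably small: about 1 to 2 power points with one run-in attack and correlation up to 0.5, rising to about 10 points with three attacks and correlation 0.7. All of these rest on assumed rates and correlations, because the documents give none.

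Bias toward no effect is conditional on two things: the 4.1 severity option is used, and erenumab lowers pre-triptan severity. In the scenarios above it then removes roughly 8% to 38% of the log odds ratio. If severity is unchanged, nothing is removed. No confirmatory conclusion is affected.

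**What to change.** 1. Reconcile SAP 4.1 with Table 9-3. Delete the three post-randomisation covariates, or confine them to analyses labelled supplementary.
2. Prespecify a run-in covariate in the month-4 responder models:
   - for pain freedom at every time point, 2-hour run-in pain freedom, for example the share of qualifying run-in attacks pain-free at 2 hours;
   - for pain relief and the most-bothersome-symptom endpoints, the matching run-in response.
3. Include a missing category. Criterion 108 guarantees a qualifying run-in attack but not a complete 2-hour record.
4. Tabulate run-in response by arm with the baseline characteristics in SAP 9.4.

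The cost is SAP wording and minor programming, with no new assessments. One consequence should be stated in the report: the odds ratio becomes conditional on the covariate and is not directly comparable with the unadjusted one.
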